Hence, reducing the impact of cognitive impairments in ABI may contribute to improvements in mood alongside BA. Therefore, the proposed study will investigate the feasibility and acceptability of two ABI-specific BA interventions, and whether one or other intervention is superior in improving mood and activity levels and how each compares to participants assessed and re-assessed on the outcome measures over the same period but with no intervention other than care as usual (waitlist condition)

Objectives

The primary objective of the MAPLES study is to determine the feasibility of two Behavioural Activation group interventions in individuals with an acquired brain injury (ABI) with low mood. This will be based on participant retention from baseline to 1-month post-intervention, acceptability of the proposed skills in the group sessions and assessments, and participant feedback from the exit interview. The two behavioural activation groups will be administered both in person and online.

A secondary objective of the MAPLES study is to evaluate whether training adults with an acquired brain injury to plan and engage in meaningful, valued, and/or enjoyable activities has detectable effects on activity level and mood compared to a waitlist control condition.

Hypotheses

There are no specific hypotheses related to the level of acceptability and feasibility of the trial whether in person or online.

Study Groups

- 1) Activity Planning Group – BA Intervention arm
- 2) Activity Engagement Group – the social group
- 3) Waitlist Group

HA-1: Relative to participants in the Waitlist Group, participants in the Activity Planning and Activity Engagement Groups will have greater increases in activity level from pre- to post-intervention and at 1 month post-intervention.

H0-1: There will be no differences in activity level from pre- to post-intervention and at 1 month post-intervention across all groups.

HA-2: Relative to participants in the Waitlist Group, participants in the Activity Planning and Activity Engagement Groups will have greater improvements in mood from pre- to post-intervention and at 1 month post-intervention.

H0-2: There will be no differences in mood from pre- to post-intervention and at 1 month post-intervention across all groups

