Individuals randomised to the Activity Engagement Group will meet weekly for 8 weeks for 1 hour and engage in various social activities such as board games, crafting, puzzles, similar to the social group in McDonald et al.'s (2008) social arm. Participants in this group will not have specific therapeutic goals and outcomes and will only be encouraged within each session to engage in activities within the group. The group will follow the below schedule:

- 1) Board games
- 2) Shirt Making
- 3) Puzzles
- 4) Painting
- 5) Trivia Day/"Pub Quiz"
- 6) Figurine painting
- 7) Origami/papercraft
- 8) Clay sculptures

MAPLES Pilot Study for Low Mood in ABI

All sessions will be administered by [name]. If participants within the Activity Engagement group strongly oppose engaging in one of the above sessions (e.g., clay sculptures) that session will be replaced with a reasonable substitute (e.g., knitting).

The online versions of the two groups will resemble the in-person groups as closely as possible. Participants will be invited to take part using video-conferencing software. Our plan at the outset is to use GoToMeeting video-conferencing software because it is easy to use, has a number of good security features and does not require participants to sign up for an account. It has also been recommended by our co-sponsor, Cambridge University Hospitals NHS Trust. We will continue to review developments in this area and may switch to an alternative service if there are advantages for data security and ease of use.

In line with the nature of the online groups and restrictions imposed by the COVID-19 crisis, the following changes will be implemented: The Activity Planning Group will focus on activities that fit with current health advice (e.g. that can take place in the home, that do not involve face-to-face contact with others, that fit with current outside home/exercise advice). The Activity Engagement group will focus on verbal games, quizzes and general conversation rather than crafts.

Waitlist Group

Individuals who are randomised to this arm of the trial will be waitlisted for 8 weeks, and then randomised again into either the Activity Planning Group or Activity Engagement Group.

Method

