All participants will complete a baseline assessment, a post-intervention assessment, and a 1-month follow-up assessment. Participants in the waitlist group will complete an additional baseline assessment prior to being re-randomised into either the Activity Planning Group or the Activity Engagement.

Randomisation Procedure

The MAPLES study will use pre-determined randomisation. Prior to any recruitment, [name] (Departmental Statistician) will generate a randomisation sequence known only to him in which the condition allocation of each consecutive consenting participant will be listed. These will be placed in sealed envelopes showing only the participant number. After conducting a baseline assessment, the researcher ([name]) will simply open the next envelope in the sequence. In order to maintain approximate parity in group size across the duration of the study (e.g. such that participants recruited later are not more likely to appear in one or other condition and such that the groups are approximately balanced at any point of study termination) randomisation will occur in subblocks of varying lengths. The researcher will not know the length of the current block over which randomisation has been balanced such that she could guess that, e.g. if the last 3 allocations had been to condition A, the next was bound to be B. At the outset of the study, [name] will similarly create randomised sequence that will determine to which of the two intervention groups each participant initially randomised to the wait-list condition will be allocated after the wait period. Again, these will be balanced over variable length subblocks and will be opened in order by the researcher after completing the second baseline assessment with Waitlist participants. In this manner, randomisation is conducted blind to any information about the participants and cannot influence or be influenced by the results of baseline assessments.

Baseline and Outcome Measures.

Demographic information will be collected from participants, including months since injury, type and cause of injury (e.g., non-TBI, hypoxia), comorbidities, Glasgow Coma Scale Scores, length of post-

MAPLES Pilot Study for Low Mood in ABI

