traumatic amnesia, duration of loss of consciousness, and data from initial assessment at Cambridgeshire Community Services, including measures of fluid and crystallised intelligence, dysexecutive syndrome, and frequency of brain injury symptoms (measured via the European Brain Injury Questionnaire). If available, we will additionally collect information on previous diagnosis of depression, as well as any psychological treatments received (e.g., Cognitive Behavioural Therapy) and any pharmacological treatments for depression. This information will be collected from the participant's medical charts. This information will only be collected if the participant has consented to it. If a participant denies access to medical information they will not be denied participation in the main study.

Baseline assessment of all below measures will be collected. Participants will be randomized into one of three conditions: 1) Activity Planning Group; 2) Activity Engagement Group, or 3) Waitlist.

Primary Outcome Measures

There is no primary outcome measure to determine its acceptability and feasibility. Determining these aspects will be based on 1) the post study questionnaire and qualitative data from the exit interviews; 2) the face validity of the intervention materials from participants, and 3) retention of participants within the trial.

The **Behavioural Activation for Depression Scale** (BADS) measures activity theorized to underlie depression according to BA (Kanter, Mulick, Busch, Berlin, & Martell, 2007, Kanter et al., 2009). Overall scores on the BADS will be used to determine the secondary objective of the trial.

Additional Measures

The **Hospital Anxiety and Depression Scale** (HADS; Zigmond & Snaith, 1983) is a widely-used measure of depression and anxiety in clinical settings.

The **Behavioural Inhibition/Behavioural Activation Scales** (BIS/BAS) measures an individual's disposition toward avoiding and engaging in activities (Carver & White, 1994).

The **Intolerance of Uncertainty Scale-Short-Form** (IUS-SF) measures an individual's degree to which they are bothered by uncertainty (Carleton, Norton, & Asmundson, 2007).

The **Impact of Events Scale-Revised** (IES-R) measures acute and routine life stress (Weiss, 2007).

The **Brain Injury Rehabilitation Trust Motivation Questionnaire-Self** (BMQ-S) measures difficulties with overall motivation in ABI (Oddy, Catran, & Wood, 2008).

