The **Motivation for Traumatic Brain Injury Rehabilitation Questionnaire** (MOT-Q) measures level of motivation for rehabilitation-related activities (Chervinsky et al., 1998)

The **Modified Outcome Measure-Participation Objective, Participation Subjective** (MOM-POPS) measures an individual's desired and actual participation in home and community activities (Brown et al., 2004).

The **Sense of Control Scale** (SCS) measures an individual's perceived ability to exert control over their life (Lachman & Weaver, 1998a, 1998b)

The **Credibility/Expectancy Questionnaire** (CEQ) measures participant expectations of treatment outcome and perceived credibility of the treatment (Deville & Borkovec, 2000). This measure will only be given at Time 1.

The **Snaith Hamilton Pleasure Scale** (SHAPS) measures an individuals' ability to experience pleasure in day-to-day activities (Snaith et al., 1995).

The **Fatigue Severity Scale-7** (FSS; Krupp et al., 1989) measures level of fatigue in patient populations.

The **Patient Health Questionnaire-9** (PHQ-9; Kroenke et al., 2001) measures symptoms of depression.

The **Generalized Anxiety Disorder-7 item Scale** (GAD-7; Spitzer et al., 2006) measures symptoms of generalised anxiety disorder such as excessive worry and irritability.

MAPLES Pilot Study for Low Mood in ABI

Neuropsychological Assessment

The below assessment will be used to characterise the population at baseline.

The ***Verbal and Spatial Reasoning Test*** (VESPAR; Langdon & Warrington, 1995) is a fluid intelligence assessment for neurological patients.

Along with the above measures, participants in the Activity Planning Group will be asked to submit a copy of their activity schedules in order to conduct exploratory analyses of what type of activities individuals with an ABI commonly engage in.

The questionnaire battery described above will be administered at baseline (Time 1), post-intervention (Time 2) and 1-month post-intervention (Time 3) either face-to-face, over the phone, via videoconferencing, using online questionnaires or via post, as per convenience for the participant. Participants who are first randomised to the waitlist condition will complete the questionnaire battery again prior to starting in the Activity Planning or Activity Engagement Group.

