Feasibility and practicality of Activity Planning vs. Activity Engagement groups, and each in-person vs. online, will be assessed in three ways: 1) through examining data on attendance and drop out and the occurrence of technical or other barriers (e.g. transport for in-person groups); 2, through a post-study questionnaire administered to all participants, and 3) semi-structured exit interviews. Semi-structured exit interviews will be conducted by a member of the research team that has not administered the intervention or conducted the assessments. Approximately 30% of participants (randomly selected) will be invited to take part in the exit interviews. The interview will cover critical aspects of the trial to ensure success of a full-scale trial, such as utility of content covered in the treatment, whether homework was sufficiently challenging and perceived to be useful, and the impact of the treatment on daily life.

After completing participation in the MAPLES study, participants will be given the option for their contact details to be retained in order to receive a summary of the study results after the results have been published. Additionally, if participants are found not to be eligible OR they have completed their participation in the MAPLES study, they will be given the option to have their contact details retained in order to be contacted about other research studies that may be of interest to them.

Analysis

Quantitative data analysis will be conducted by [name] and supervised by senior members of the research team and by the trial statistical consultant ([name]). First, participants who completed a group in-person will be separated from those who completed their group online in order to compare differences between method of assessment. A general linear model using the BADS across the multiple assessments points will be used to determine the effectiveness of the intervention. In line with our hypotheses, it is predicted that the Activity Planning Group will show improvements in activity level and greater reductions in low mood relative to the Activity Engagement Group and Waitlist group. Effect sizes will be estimated based on the trial data. Exploratory analyses investigating the relationship of the secondary questionnaires to outcome will be conducted using correlation analyses.

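### The plan does not say how baseline BADS enters the efficacy model; if read as a change contrast with free baseline means, it gives up precision that baseline adjustment would recover

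*Combined protocol and SAP*

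**What the plan says.** The Analysis section of the combined protocol and SAP gives the whole model in one sentence: "A general linear model using the BADS across the multiple assessments points" is to be used to judge whether the intervention works. It names no contrast, covariate or covariance structure. A later sentence says that effect sizes will be estimated from the trial data.

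Four other places bear on how that sentence should be read:

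- **Primary Outcome Measures:** "Overall scores on the BADS will be used to determine the secondary objective of the trial". BADS therefore serves the efficacy objective. The primary objective is feasibility.
- **Neuropsychological Assessment (end of section):** the battery is scheduled with baseline as Time 1, the end of the intervention as Time 2 and one month later as Time 3. Baseline is thus one of the assessment points.
- **Hypotheses:** the two intervention groups, relative to Waitlist, "will have greater increases in activity level from pre- to post-intervention and at 1 month post-intervention". The mood hypothesis has the same form.
- **Randomisation Procedure:** "After conducting a baseline assessment, the researcher ([name]) will simply open the next envelope in the sequence". The envelope for the second randomisation is likewise opened only after the second baseline.

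Under Waitlist Group, participants in that arm "will be waitlisted for 8 weeks, and then randomised again into either the Activity Planning Group or Activity Engagement Group". No section names baseline BADS as a covariate, says that it will not be one, or constrains the arms to a common baseline mean.

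**The concern.** Taken together, these places describe a repeated-measures general linear model with baseline as one of the responses, judged by group-by-time. With free baseline means and one follow-up, that term is a comparison of change scores. A change score subtracts the whole baseline value, whatever the correlation, and so carries baseline noise into the estimate. Adjustment subtracts only the part of baseline that predicts follow-up.

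Each baseline precedes its own allocation, so it is a valid covariate. Allocation is not described as stratified on BADS, so only the analysis can deal with chance imbalance. At stake is the width of the intervals for the secondary comparisons and for the effect sizes that a full trial would inherit. The Analysis section also begins by separating in-person from online participants. If that split is carried into the model, each comparison becomes smaller still.

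**Working it through.** The documents state no sample size, SD, effect size, significance level or correlation, so there is no figure to reproduce. What follows is an illustration under stated assumptions.

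**Inputs**
- From the documents: baseline measured before allocation; approximately equal arms; one untreated follow-up for Waitlist, at the end of the 8-week wait.
- Assumed: r of 0.4 to 0.7 (0.3 to 0.7 in some checks); equal SDs at baseline and follow-up, scaled to 1; 8 to 20 per arm for the small-sample checks.

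**One follow-up, large samples**
- Change contrast with free baseline means, variance factor: 2(1−r).
- Baseline-adjusted contrast (ANCOVA), variance factor: 1−r².
- Ratio, ANCOVA to change: (1−r²) / [2(1−r)] = (1+r)/2.

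| r | change | ANCOVA | ratio |
|---|---|---|---|
| 0.4 | 1.20 | 0.84 | 0.70 |
| 0.5 | 1.00 | 0.75 | 0.75 |
| 0.6 | 0.80 | 0.64 | 0.80 |
| 0.7 | 0.60 | 0.51 | 0.85 |

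The variance is 15% to 30% lower, equivalent to 1/0.85 = 1.18 to 1/0.70 = 1.43 times the participants.

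**Cost of estimating the slope in a small trial**

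With n per arm in a two-arm contrast, the ANCOVA variance is multiplied by 1 + 1/(2n−4). At n = 10 this is 1 + 1/16 = 1.0625.
- r = 0.4: 0.70 × 1.0625 = 0.74.
- r = 0.7: 0.85 × 1.0625 = 0.90.
- Break-even: (1+r)/2 × 1.0625 = 1 gives r = 2/1.0625 − 1 = 0.88.

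The break-even is about 0.85 at 8 per arm, 0.93 at 15 and 0.95 at 20. A simulation at 10 per arm (8,000 runs per setting) gave ratios of 0.69, 0.79 and 0.89 at r = 0.3, 0.5 and 0.7. The formula gives 0.69, 0.80 and 0.90.

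**Unequal SDs**

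With baseline SD s₀ and follow-up SD s₁, change variance minus ANCOVA variance is (s₀² + s₁² − 2r·s₀·s₁) − s₁²(1−r²) = (s₀ − r·s₁)². The large-sample gain is therefore zero when r = s₀/s₁. For example, with SDs 0.7 and 1.0 and r = 0.7, change gives 0.49 + 1 − 0.98 = 0.51 and ANCOVA gives 1 − 0.49 = 0.51.

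**Two follow-ups averaged (Planning versus Engagement)**

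Assume the same r between every pair of visits. The change factor is (1+r)/2 + 1 − 2r and the ANCOVA factor is (1+r)/2 − r². The ratios are 0.56/1.05 = 0.53, 0.50/0.75 = 0.67 and 0.36/0.45 = 0.80 at r = 0.3, 0.5 and 0.7, before any small-sample cost.

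**Other readings of the same sentence**
- *Group main effect averaged over baseline and one follow-up.* This estimates half the effect, with equivalent variance factor 2(1+r). The ratio is (1−r)/2, or 0.35, 0.25 and 0.15 at r = 0.3, 0.5 and 0.7, so the loss is larger.
- *Baseline kept as a response with arm means constrained equal.* The loss essentially vanishes.

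**The case against.** The strongest reply is that the text is silent. ANCOVA is itself a general linear model, and an analysis of later scores adjusted for baseline also uses BADS across assessment points. A reader might infer that the plan has chosen change scores and rejected adjustment, but no section says so. Nor is listing baseline among the responses a fault in itself, since the common-baseline model does exactly that. Any loss comes from leaving the arm means free at baseline. This stands, and it limits the point to the natural reading of an unspecified model.

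A second reply is that adjustment does not help at every correlation below 1. That also stands. The claim holds only in large samples, and even there the gain is nil where r equals the ratio of baseline to follow-up SD. Participants are selected for low mood, so a narrower spread at baseline is possible.

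A third reply is that the hypotheses are worded as change, so a change contrast answers the question asked. It does, and without bias over the randomisation. But the baseline-adjusted difference at follow-up targets the same treatment effect, because arms formed by randomisation share a baseline mean in expectation. The wording therefore does not require the less precise estimator.

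Finally, the trial is a feasibility pilot. A reader might infer that its main conclusions are weakened. They are not, because BADS is not used to judge feasibility. How small the trial is cannot be quantified from the text either; only the pilot label suggests it.

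**Conclusion.** The point holds as a low-cost improvement to an underspecified model. As written, the plan reads as a group-by-time comparison with baseline as a response, and nothing adjusts for baseline or equates its means. If the means are free, the adjusted estimate with one follow-up has about 0.70 to 0.85 of the variance in large samples, or about 0.74 to 0.90 at 10 per arm. At that size there is no gain above about r = 0.88. These figures rest on equal SDs and on an assumed r of 0.4 to 0.7 and an assumed sample size, none of which the documents supply.

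The consequence is wider intervals and more exposure to chance imbalance for the secondary efficacy objective and its effect sizes. The documents do not support a claim of bias or any effect on the feasibility conclusions.

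**What to change.** Amend the Analysis section to state the role of baseline and the contrasts:

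1. **Response and covariate.** Follow-up BADS is the response and pre-allocation BADS is a covariate. Equivalently, keep baseline as a response but constrain its mean to be equal across arms.
2. **Contrasts with Waitlist.** Compare each intervention arm at post-intervention with Waitlist at the end of the wait, adjusted for the first baseline. This is a single time point. Waitlist participants are re-randomised into a group after it, so they have no untreated score at the one-month visit, whichever model is used.
3. **Planning versus Engagement.** Run this as a separate analysis with both follow-ups. Adjust for the baseline taken just before each participant's allocation to a group, which is the second baseline for those coming from Waitlist. Keeping it separate avoids one model in which the same people appear both as untreated and as treated.
4. **Mood.** Apply the same approach to whichever mood scale is analysed, with its own baseline. The plan lists both the HADS and the PHQ-9 and does not say which tests the mood hypothesis, so it should name one.

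The cost is a short paragraph written before the data are examined, and one degree of freedom per covariate. No new data are needed, because both baselines are already scheduled.

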Here, we will investigate the benefits of BA primarily in people who have sustained traumatic brain injuries (TBI) and, for the first time in ABI, examine the efficacy of group rather than individual therapy. There are clear economic advantages to group, compared with individual, therapy and, when they work well, the supportive dynamics of groups of people with similar challenges can enhance therapeutic effects. It might be expected that conventional BA, in which people learn about the importance of activity engagement, of scheduling activities in everyday life and of overcoming barriers and resisting avoidant behaviour would lead to more generalised and lasting gains than simply engaging in rewarding activities without such knowledge and skill acquisition. However, it is also possible that cognitive problems (e.g. in remembering details) may undermine these gains. Accordingly, we will compare this conventional BA group ("activity planning") with a second intervention group ("activity engagement") in which participants will be encouraged to engage in potentially rewarding activities (crafts, games, social discussion) but which will not emphasise planning and scheduling activities outside of the group. Here it is possible that, through positive experiences of engagement, participants implicitly or explicitly generalise to increase activity levels in daily life. This second intervention also serves to make it clearer, should the "activity planning" be associated with

MAPLES Pilot Study for Low Mood in ABI

greater gains in activity and mood that it is likely attributable to the conventional BA component rather than more general group dynamics.

Cognitive impairments in ABI such as inability to override habits in favour of new behaviours may pose barriers to BA's success. Incorporating cognitive training developed specifically for ABI may enhance the effectiveness of BA. For example, Goal Management Training (GMT; (Levine et al., 2000, 2011) is designed to help individuals with ABI overcome habits, generate solutions, and attain goals. GMT is well-suited to groups, with participants providing support and feedback to one another, alongside "homework" designed to encourage understanding and application of skills (Levine et al., 2011).

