Clinicians within the NHS will be responsible for the initial contact with clients and reviewing their medical information with respect to the inclusion/exclusion criteria. No personal information will pass to the research team until a potential participant makes contact with the researchers or, with the participant's consent, the clinical team pass contact details to the research team. Alongside contact information, the research team will ask eligible participants for consent to access their NHS medical records for details of the nature of their injury such as injury type, and location within the brain. Access to medical records will be part of the clinician consent process (in brief) as well as part of the consent process with the research team. Access to medical records is necessary to describe the demographic represented in our sample, as well as to determine whether injury-related variables (e.g., frontal vs non-frontal lobe injuries) affect outcome in the trial. Participants who refuse to give access to their medical records to the research team will still be welcome to participate.

Participants identified through non-NHS ABI charities

A member of the research team will send out flyers to ABI charity groups so that potential participants can contact members of the research team. These flyers can be posted at the physical venue, online through charity group social media accounts, or handed out by staff members. Additionally, the Invitation Letter can be emailed directly to charity group members with a direct link to consent to being contacted. The non-NHS invitation letter will be created through both Qualtrics (local University server) and JATOS, an internal online server only accessible by the MRC CBU. Upon entering their contact details, the MAPLES research team will receive a notification that someone has consented to be contacted and thus will be followed up by the MAPLES research team. Participants recruited through this manner will have the opportunity to ask further questions prior to being screened and reminded

MAPLES Pilot Study for Low Mood in ABI

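### The exploratory correlations name neither arm nor baseline BADS; adjust for both, and add one estimation-only Planning v Engagement by VESPAR term

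*Combined protocol and SAP*

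**What the plan says.** The Analysis section of the protocol plans a general linear model on BADS over the assessment points and names no covariate or interaction. For everything else quantitative it says: "Exploratory analyses investigating the relationship of the secondary questionnaires to outcome will be conducted using correlation analyses". It does not say whether these correlations are pooled or within arm, or whether the questionnaires are taken at baseline, after treatment or as change.

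Background and Rationale first suggests that conventional behavioural activation may give the more lasting gains. It then adds that "it is also possible that cognitive problems (e.g. in remembering details) may undermine these gains", and goes straight on to the comparison of Activity Planning with Activity Engagement. The same paragraph gives a second reason for the Engagement arm: to separate the behavioural activation component from general group effects. Neither Objectives nor Hypotheses mentions effect modification by cognition.

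The one cognitive test given to participants is VESPAR, which "is a fluid intelligence assessment for neurological patients". Under Neuropsychological Assessment its use is stated as: "The below assessment will be used to characterise the population at baseline". It is listed apart from the questionnaires, so the correlation sentence does not reach it.

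Baseline and Outcome Measures also lists chart data "including measures of fluid and crystallised intelligence, dysexecutive syndrome, and frequency of brain injury symptoms", but on a condition: "This information will only be collected if the participant has consented to it". The section on participants identified through NHS services wants record access "to determine whether injury-related variables (e.g., frontal vs non-frontal lobe injuries) affect outcome in the trial", and the Analysis section gives no method for that either.

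**The concern.** In a three-arm trial, a correlation that ignores arm mixes within-arm and between-arm association. Three things can go wrong.

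- Two measures taken after treatment, or two change scores, can correlate because treatment moved both, with no link between them inside any arm. The result would look like a mechanism or a predictor.
- A baseline characteristic that matters in one arm and not in the others shows up as a weak overall relation. The same pooled value can arise from a characteristic that is merely prognostic.
- Without baseline BADS in the model, a questionnaire that overlaps with BADS at entry will appear to predict later BADS, because BADS predicts itself.

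What is at stake is the use of the pilot to shape a full trial. The list of apparent predictors could mislead, and the cognition issue raised in the rationale would get no estimate although a baseline cognitive score is in hand.

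**Working it through.** The documents give no sample size, alpha, power, SD or assumed effect for these analyses, so there is no figure of the plan's own to reproduce. All sizes below rest on assumptions stated at each step. Arms are taken as equal in size, in line with the approximate balance that the randomisation section aims for.

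**1. Correlation created by arm alone.** Take two post-treatment (or change) measures with within-arm SD 1 and no within-arm correlation. Both active arms shift each measure by d; Waitlist is not shifted. Two thirds of participants are shifted, so the between-arm variance of each measure, and the covariance of the two, is v = (2/3)(1/3)d² = (2/9)d². The pooled correlation is r = v/(1 + v).

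- d = 0.8: v = 0.142, r = 0.142/1.142 = 0.12
- d = 1.0: v = 0.222, r = 0.222/1.222 = 0.18

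This does not apply to a questionnaire taken before randomisation, which is independent of arm in expectation.

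**2. A baseline relation that differs by arm.** With variables standardised within arm and equal arm means, the pooled r is the mean of the arm values. A slope of 0.5 in Planning and 0 in the other two gives (0.5 + 0 + 0)/3 = 0.17; a simulation with 200,000 per arm gave 0.168.

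**3. Can a pooled correlation separate prognosis from moderation?** Take Planning and Engagement only, with a standard normal predictor and residual SD 1.

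- Slope 0.3 in both arms: r = 0.3/√(1 + 0.3²) = 0.3/√1.09 = 0.29 pooled, and 0.29 in each arm.
- Slope 0.6 in Planning and 0 in Engagement: the pooled slope is 0.3 and the outcome variance is 1 + 0.36/2 = 1.18, so r = 0.3/√1.18 = 0.28 pooled. Within arms it is 0.6/√1.36 = 0.51 in Planning and 0.00 in Engagement.

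The pooled values, 0.29 and 0.28, cannot be told apart in practice; the arm-specific values can.

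**4. Number of looks.** Thirteen questionnaires are listed under Additional Measures. If each were tested once at 5% and all were independent, the chance of at least one false positive would be 1 − 0.95¹³ = 49%. The credibility questionnaire is given only at Time 1, so twelve apply after treatment: 1 − 0.95¹² = 46%. These are illustrations: the plan states no test level, and several scales overlap in content, so independence does not hold.

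**5. Precision of the proposed VESPAR term.** The 95% half-width for the difference in slopes, in outcome SD per VESPAR SD with residual SD 1 and n per intervention arm, is about 1.96√(2/n).

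| Assumed n per arm | Half-width | Power for correlation 0.5 v 0 |
|---|---|---|
| 10 | 0.88 | 18% |
| 20 | 0.62 | 36% |
| 30 | 0.51 | 52% |

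Power is from the Fisher z comparison of the two arm correlations, SE = √(2/(n − 3)), two-sided 5%. About 56 per arm would be needed for 80% power at 0.5 v 0. None of these figures allows for clustering by therapy group or for separating in-person from online participants; both would reduce precision.

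**The case against.** The strongest case against acting is that this is a feasibility pilot and the analyses are labelled exploratory. The rationale can be read as saying that the Planning v Engagement comparison in a brain-injured sample is itself the test of whether cognitive problems cancel the benefit. On that reading no moderation analysis is owed, and leaving it to the full trial is a legitimate choice. This stands to the extent that cognitive moderation is not an objective or hypothesis and is only one of two reasons for the Engagement arm. It does not remove the gap: a difference in arm means cannot show whether cognition is the cause.

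Second, the Analysis section does not say that the correlations are pooled. That is right. Pooling is the literal reading of a sentence with no arm term, and the defect is that the text leaves it open.

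Third, the arm-induced correlation needs both measures to respond to treatment. That also stands. A reader might infer that any reported predictor could merely reflect allocation; for baseline questionnaires the documents do not support that.

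Fourth, VESPAR is a weak stand-in. The protocol's example is remembering details, VESPAR measures fluid reasoning, and no memory test is listed. Excluding severe cognitive disability narrows its range. The chart measures come from one service's initial assessment and depend on consent, so they are likely to be incomplete for charity and panel recruits. All of this stands, and it limits what the VESPAR estimate can mean.

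Fifth, interaction models for every questionnaire would multiply imprecise estimates. This stands, and the fix avoids it.

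**Conclusion.** The exploratory analysis is under-specified and, read literally, uses the wrong method for three randomised arms. Under the stated assumptions, arm alone can produce a pooled r of 0.12 to 0.18 between post-treatment or change measures, and a relation of 0.5 confined to Planning shrinks to about 0.17. The sizes depend on assumed shifts and slopes; the direction of the problem does not.

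A reader might go further and infer that the trial cannot address, from the data it collects, whether cognition undermines Planning gains. The documents do not support that. Baseline VESPAR, allocation and repeated BADS are all collected, so the term can be fitted with no new data. What is missing is the analysis. Nor is this a failure to meet a stated objective, since cognitive moderation appears only in the rationale. Even after the fix, the pilot will probably not settle who benefits; it will give an honest estimate with a wide interval.

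**What to change.** Replace the correlation sentence in the Analysis section with the following.

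- Regress BADS at the end of the first 8-week period on baseline BADS, arm and the baseline questionnaire, one questionnaire at a time. The coefficient is still an average over arms and should be described as such.
- Relate change to change only within arm or with adjustment for arm.
- Report how many measures were examined and at which time points.
- Add one exploratory Planning v Engagement by baseline VESPAR term to the BADS model. Report the slope difference with its 95% CI and make no significance claim. State that VESPAR measures fluid reasoning and not memory.
- Do not fit interaction models for the other questionnaires.

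The same arm-adjusted regression would supply the missing method for the injury-related variables. If the sponsor prefers not to add the VESPAR term, the plan should say that cognitive moderation is left to the full trial.

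The cost is a few sentences and a little more analysis, with no new data. The downside is a wide interaction interval, about ±0.9 to ±0.5 SD per SD at an assumed 10 to 30 per arm and wider with clustering by therapy group. It should be shown as it is.
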